### 7.5.7. Suicidal Risk Monitoring

Sirukumab is considered to potentially be a CNS-active drug. There has been some concern that some CNS-active drugs may be associated with an increased risk of suicidal thinking or behaviour when given to some patients with certain conditions. Although this drug or other similar drugs in this class have not been shown to be associated with an increased risk of suicidal thinking or behaviour when given to this patient population,

GSK considers it important to monitor for such events before or during clinical studies with compounds such as this.

Subjects being treated with sirukumab should be monitored appropriately for suicidal ideation and behaviour or any other unusual changes in behaviour. Consideration should be given to discontinuing sirukumab in subjects who experience signs of suicidal ideation or behaviour.

Suicidal ideation and behaviour will be assessed at baseline and at the time points indicated in Time and Events [Table 2](#) and in Time and Events [Table 3](#) using the patient-reported outcome version of the C-SSRS [[Mundt, 2010](#)].

### **7.5.8. Tuberculosis Evaluation**

A QuantiFERON-TB Gold Test will be performed at Screening. This test can be performed at any time during the study if TB is suspected.

A TB questionnaire will be completed at the times specified in Section [7.1](#), Time and Events Tables. This questionnaire will evaluate signs and symptoms of active TB in order to aid in the early detection of TB reactivation or new TB infection during the study. The following series of questions is suggested for use during the TB evaluation:

- “Have you had a new cough of >14 days’ duration or a change in a chronic cough?”
- “Have you had any of the following symptoms:
  - Persistent fever?
  - Unintentional weight loss?
  - Night sweats?”
- “Have you had close contact with an individual with active TB?” (If there is uncertainty as to whether a contact should be considered “close,” a physician specializing in TB should be consulted.

If the evaluation raises suspicion that a subject may have TB reactivation or new TB infection, study drug administration should be interrupted and an immediate and thorough investigation should be undertaken, including, where possible, consultation with a physician specializing in TB.

Investigators should be aware that TB reactivation in immunocompromised subjects may present as disseminated disease or with extrapulmonary features. Subjects with active TB must immediately discontinue study drug and be referred to a physician specializing in TB for appropriate treatment.

Subjects who experience close contact with an individual with active TB during the conduct of the study must have a repeat chest radiograph, a repeat QuantiFERON-TB Gold test and, if possible, referral to a physician specializing in TB to determine the subject’s risk of developing active TB and whether treatment for latent TB is warranted.

Study drug administration should be interrupted during the investigation. A positive QuantiFERON-TB Gold test result should be considered detection of latent TB. If the result is indeterminate, the test should be repeated. If recommended, treatment for latent TB must be initiated prior to the administration of further study drug. Subjects who discontinue treatment for latent TB prematurely or who are noncompliant with therapy must immediately discontinue further administration of study drug and should return for all subsequent scheduled study visits.

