#### **5.4.2. Discontinuation of Study Drug**

Permanent discontinuation of study drug will not require the subject to be withdrawn from the study. Subjects should continue where possible to be followed and disease status assessed. Upon permanent discontinuation of subcutaneously-administered blinded sirukumab or matching placebo, corticosteroid dose and treatment will be at the discretion of the investigator.

Study drug (subcutaneously-administered blinded sirukumab or matching placebo) must be permanently discontinued for any of the following:

1. The investigator (in consultation with the medical monitor) believes that for safety reasons (e.g., adverse event) it is in the best interest of the subject to stop treatment.
2. Severe allergic reaction or anaphylactic reaction resulting in bronchospasm with wheezing, or dyspnea requiring ventilatory support, or symptomatic hypotension with a > 40 mmHg decrease in systolic blood pressure that occurs following study drug administration.
3. Reaction suggestive of serum sickness occurring 1-14 days after study drug administration. These may be manifested by symptoms of myalgias, arthralgias, fever, rash, pruritus, facial, hand, or lip edema, dysphagia, urticaria, sore throat, and/or headache.

4. Adverse events (AEs) or laboratory abnormalities indicative of safety concerns which are significant enough to discontinue study drug in the opinion of the investigator.
5. Pregnancy.
6. Liver function abnormalities as specified in Section 5.4.3.
7. Opportunistic infection, ie, an infection by an organism that usually causes disease only in a host whose resistance is lowered (eg, Pneumocystis jirovecii, coccidioidomycosis, Mycobacterium avium).
8. Active or latent TB.
9. Malignancy, excluding nonmelanoma skin cancer.
10. Demyelination, either central or peripheral.
11. Two confirmed consecutive absolute neutrophil counts of  $<0.5 \times 10^9$  cells/L.
12. Two confirmed consecutive platelet counts  $<50 \times 10^9$  cells/L.
13. Acute diverticulitis requiring antibiotic treatment.
14. Gastrointestinal perforation.

Subjects must **not** receive blinded subcutaneous sirukumab or matching placebo during the course of a serious infection. Subjects who temporarily discontinue blinded sirukumab or matching placebo due to an infection or other reasons should continue to follow the prednisone taper schedule.

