Safety Assessments															
Physical Examination 	x									x		x	x	x	x
Vital Signs 	x	x	x	x	x	x	x	x		x	x	x	x	x	x
TB evaluation 	x	x	x	x	x	x	x	x		x	x	x		x	
Height and weight	x											x	x	x	
Adverse Events	x	x	x	x	x	x	x	x		x	x	x	x	x	x
C-SSRS 	x	x	x	x	x	x	x	x		x	x	x	x	x	x
Laboratory Assessments															
Hematology	x	x	x	x	x	x	x	x		x	x	x	x	x	

	Wk 0/(Wk 52 of Part A)	Wk2±5d	wk 4±5d	wk 8±5d	wk 12±5d	wk 16±5d	wk 24±5d	wk 36±5d	wk 48±5d 	wk 52±5d	wk 76±5d	wk 104±5d	Flare	Early Withdrawal	Follow Up
Serum chemistry	x	x	x	x	x	x	x	x		x	x	x	x	x	
CRP	x	x	x	x	x	x	x	x		x	x	x	x	x	
ESR	x	x	x	x	x	x	x	x		x	x	x	x	x	
Lipid panel (fasting)	x				x	x	x	x		x	x	x	x	x	
Hemoglobin A1c	x				x	x	x	x		x	x	x	x	x	
Pregnancy Test 	U		U	U	U	U	U	U	U	U	U	U		U	U
PK 	x				x					x		x	x	x	x
Immunogenicity 	x				x					x		x	x	x	x
Exploratory Lab Assessments															
IL-6 measurements	x														
Blood Biomarkers & exploratory markers	x														
Blood and Urine Markers, Transcriptomics (optional)	x														
Exploratory US Imaging															
Ultrasound imaging 													x		

1. Visit only to dispense IP; no assessments are required.
2. PROs to be completed by subjects before other clinically evaluated assessments or blood draws and before the administration of study drug. At visits where subject is fasting for blood draws, the option exists to perform blood draws prior to completing PROs as necessary to end the fast. HAQ-DI administered only to sub-set of subjects with PMR. PGA assessed using PtGA (subjects) and PhGA (physicians, after subject completion of questionnaires and after conducting patient assessments).
3. Brief physical exam.
4. Measure in a semi-supine position after 5 minutes rest; includes blood pressure, temperature and heart rate.
5. Suggested questions (see Section 7.5.7). A QuantiFERON-TB Gold Test (or if not approved at the site, a tuberculin skin test) should be performed at any time during the study if TB is suspected.

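### In Part A, Protocol 7.5.8 allows blinded drug to resume after latent-TB treatment starts, which 5.4.2 item 8 forbids, and the path taken decides treatment-failure status

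*Protocol*

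**What the plan says.** Protocol 5.4.2 opens its stopping list with "Study drug (subcutaneously-administered blinded sirukumab or matching placebo) must be permanently discontinued for any of the following". Item 8 on that list is "Active or latent TB". Treated subjects are not excepted.

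Protocol 7.5.8, in its paragraph on close contact with a TB case, interrupts drug during the work-up and says "A positive QuantiFERON-TB Gold test result should be considered detection of latent TB". It continues: "If recommended, treatment for latent TB must be initiated prior to the administration of further study drug". The only stop it then orders is conditional: "Subjects who discontinue treatment for latent TB prematurely or who are noncompliant with therapy must immediately discontinue further administration of study drug".

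The two outcomes carry different steroid rules, both in 5.4.2. After a permanent stop: "Upon permanent discontinuation of subcutaneously-administered blinded sirukumab or matching placebo, corticosteroid dose and treatment will be at the discretion of the investigator". After a temporary one: "Subjects who temporarily discontinue blinded sirukumab or matching placebo due to an infection or other reasons should continue to follow the prednisone taper schedule".

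SAP 4.6.1 counts a permanent stop of subcutaneous drug before the Week 52 visit as treatment failure and says that a temporary hold is not a permanent stop. SAP 4.6.2.1 turns failure into absence of sustained remission, and Protocol 9.4.1 likewise records subjects who discontinue treatment as non-responders.

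**The concern.** The two sections give different answers for one kind of Part A subject: latent TB detected on study, treatment started and followed. A site reading the stopping list ends blinded drug. A site reading the dedicated TB section may give more. Neither section refers to the other or says which prevails.

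TB reactivation is a listed risk for this drug class (Protocol 4.6.1), so a safety instruction should have one reading. The data are affected too, because the site's choice changes how the subject is classified for the primary endpoint, the steroid regimen the subject follows and, after termination, possibly whether the subject is counted at Week 52.

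**Working it through.** **Side by side, blinded drug in Part A**

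| Situation | Protocol 5.4.2 | Protocol 7.5.8 |
|---|---|---|
| Active TB | Permanent stop | Immediate stop |
| Latent TB, treatment abandoned or not followed | Permanent stop | Immediate stop |
| Latent TB, treated and compliant | Permanent stop | Further drug allowed once treatment has started |

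The sections part only in the last row. Stopping there satisfies both; resuming satisfies 7.5.8 and breaches 5.4.2. The 5.4.2 list names blinded drug only, so for open-label sirukumab in Part B only 7.5.8 applies and nothing conflicts.

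**What follows from each path**

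| | Permanent stop | Hold, then resume |
|---|---|---|
| SAP 4.6.1 | Treatment failure | Not a failure on this ground |
| Prednisone (Protocol 5.4.2) | Investigator's discretion | Stays on the taper |
| Week 52 summary (SAP 8.1), Week 52 not reached | Included as a failure if stopped before 10 October 2017 | Excluded if still on study at termination |

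The steroid row can also change cumulative prednisone dose, since SAP 4.6.3.1 keeps data after subcutaneous drug is stopped for subjects who remain in the study.

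**Scale**

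The plan attaches no figure to latent TB. For context, its 96% planning power for 51 versus 34 subjects at 70% versus 30% (Protocol 9.2.2) reproduces at 96.5% with a two-sided pooled-variance normal approximation. No figure in the plan is in dispute.

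Inputs: planned arm sizes of 51 (A, B) and 34 (C, D, E), from Protocol 4.2.1. The shift in an arm's rate when one subject otherwise in sustained remission becomes a failure is 1/n:

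- n = 51: 1/51 = 2.0 points
- n = 34: 1/34 = 2.9 points

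The number of subjects per arm in the post-termination summary is not given. Taking 20 or 10 as assumptions:

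- n = 20: 1/20 = 5.0 points
- n = 10: 1/10 = 10.0 points

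For a subject who had not reached Week 52, the path adds or removes a failure from the denominator. With an assumed rate of 50%:

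- 10/20 = 50.0% becomes 10/21 = 47.6%
- 5/10 = 50.0% becomes 5/11 = 45.5%

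**How many subjects**

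The documents give no count. Entry requires a negative QuantiFERON and no history of latent TB (Protocol 5.1). On study, the test is not scheduled; it follows close contact with a TB case, or under the Time and Events Tables it "should be performed at any time during the study if TB is suspected". Few detections are likely.

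**The case against.** A reader might infer that the two sections impose duties that cannot both be met. The documents do not support that. Section 7.5.8 sets a precondition for further dosing and never requires it, so a site that stops for good breaches nothing. The defect is narrower: one section allows what the other forbids.

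The restart sentence also has harmless uses. It can apply to open-label drug in Part B, and perhaps to a close contact given treatment without a positive test. Both readings are fair, but the sentence is not limited to them. It directly follows the definition of a positive test as latent TB and speaks of study drug in general, and Part A's Table 2 schedules a TB evaluation at every visit.

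It can be said that item 8 is the stricter rule and was meant to govern. The Amendment 1 log supports this: item 8 previously caught latent TB only where treatment was dropped or not followed, which is the logic still in 7.5.8. That is a good reason to align 7.5.8 with item 8. The conflict itself rests on the current text alone.

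Finally, SAP 4.6.1 classifies what actually happened, so no subject's status is undefined in the analysis. That stands. The weakness is that similar subjects at different sites could be handled, and therefore classified, differently.

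**Conclusion.** The inconsistency is real and confined to blinded drug in Part A. For a treated, compliant subject with latent TB, 7.5.8 opens a path that 5.4.2 item 8 closes, and the choice affects failure status, steroid handling and, before Week 52, inclusion in the summary.

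The effect is probably small. One subject is worth 2.0 or 2.9 points at planned size, and more only if the post-termination denominators are as low as the assumed 10 or 20. These shifts assume a subject who otherwise met every remission criterion. SAP 1.1 drops statistical analysis of efficacy, so only descriptive summaries can move. A reader might infer that an efficacy conclusion is at risk; the documents show no affected subject and plan no efficacy test. The point is worth correcting because it concerns a safety stopping rule and the correction is cheap.

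Minor note: Table 7 interrupts drug at ALT or AST of 3×ULN or more, while Appendix 3 lets an asymptomatic subject with ALT of 3 to below 8×ULN and bilirubin below 2×ULN continue under weekly monitoring. A reader might see a second conflict of equal weight. It is weaker: holding satisfies both, Section 5.4.3 itself foresees temporary discontinuation, its flowcharts (not available here) may set precedence, and neither action is a permanent stop that would change failure status.

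**What to change.** **Protocol text.** Leave 5.4.2 item 8 as it is. In 7.5.8, state that latent TB detected on blinded drug means permanent discontinuation under 5.4.2 item 8 and referral to a TB physician, and limit the restart sentence to open-label sirukumab in Part B. The cost is a few lines of wording. The downside is that a treated, compliant subject loses blinded drug that he or she might have continued.

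**Report.** As the study was terminated on 10 October 2017, this is the practical step. SAP 9.2.3 already lists QuantiFERON results and SAP 5.1 lists reasons for stopping subcutaneous drug, but neither specifies a link between the two. Add one flag for each on-study positive QuantiFERON: drug stopped, or resumed after treatment started. If a Part A subject resumed, also show the Week 52 proportion with that subject counted as a failure. This works only for subjects who resumed; for one who stopped, the outcome under resumption was never observed.

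**Liver note.** After checking the 5.4.3 flowcharts, give Table 7 and Appendix 3 the same action and say whether it applies to a rise in AST alone.

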#### **7.5.9. Chest Radiograph**

A chest radiograph will be performed at the Screening visit only for the detection of TB. A chest radiograph taken up to 3 months prior to Week 0 may be used to qualify as the screening radiograph.

### **7.6. Pharmacokinetics and Immunogenicity**

Blood samples for PK analysis of sirukumab serum concentrations and for analyses of antibodies to sirukumab will be collected at the time points specified in Section 7.1, Time and Events Tables. The actual date and time of each blood sample collection will be recorded. Blood samples for PK analyses of sirukumab serum concentrations must be drawn **prior** to the administration of study drug.

At visits where sirukumab serum concentrations and antibodies to sirukumab will be evaluated, one blood draw of sufficient volume will be used to divide the sample into 3 aliquots, one each for sirukumab serum concentrations and antibodies to sirukumab plus a back-up.

PK analyses of sirukumab serum concentrations and anti-sirukumab antibodies will be performed using validated bioanalytical assays by Janssen Research and Development under the control of PTS-DMPK/Scinovo, GlaxoSmithKline, the details of which will be included in the SPM.

Processing, storage and shipping procedures are provided in the SPM.

### **7.7. Biomarkers/Pharmacodynamic Markers**

#### **7.7.1. Exploratory Biomarkers**

Blood samples will be taken at the times indicated in Time and Events [Table 2](#), Section 7.1 for assessment of changes in the biomarkers of bone formation or resorption, CTX1 and P1NP, and for changes in biomarkers indicative of Th1 and Th17 cell function, IFN- $\gamma$  and IL-17A. An additional sample should be taken at the time of onset of disease flare when applicable for assessment of IFN- $\gamma$  and IL-17A.

## 7.7.2. Optional Exploratory Biomarkers

Subjects will also have the option to provide blood and urine samples for future evaluation of biomarkers related to GCA disease activity and transcriptomic analyses to further elucidate the biology of the disease. These samples will be stored in a biobank for a period of up to 5 years. Provision of these samples is optional and is not required for participation in the study.

## 7.7.3. Pharmacodynamic Markers

Blood samples will be taken at the times indicated in Time and Events [Table 2](#), Section [7.1](#) for assessment of changes in free and total IL-6 as a pharmacodynamic marker of sirukumab activity. Analyses of serum IL-6 levels will be performed using validated assays by Janssen Research and Development

## 7.8. Genetics

A blood sample for genetic research will be collected from consenting subjects at the baseline visit. Refusal to participate in the genetic research will not preclude the subject from participating in the study.

## 7.9. Exploratory Ultrasound Imaging

### 7.9.1. Background and Rationale

The results of three recent meta-analyses have provided evidence to support the utility of US imaging in the diagnosis of GCA [[Ball](#), 2010; [Arrida](#), 2010; [Karassa](#), 2005]. Additional data from a multicenter study, TABUL (Temporal Artery Biopsy versus ULtrasound), conducted at centers trained in US imaging techniques, also support the diagnostic utility of US in GCA [[Luqmani](#), 2015]. However, the role of US imaging in the assessment of GCA disease activity remains unclear. Available evidence consists of results from a study which found persistent abnormalities suggestive of an association with relapse when GCA patients were assessed by ultrasound imaging every 2-4 weeks [[De Miguel](#), 2012]. Permanent visual loss is also associated with the presence of abnormal sonographic features of cranial and extra-cranial arteries [[Schmidt](#), 2008; [Schmidt](#), 2009; [Czihal](#), 2012]. A recent prospective observational study has demonstrated that ultrasound can be informative in distinguishing potential flares from exacerbations of unrelated headache in patients with diagnosis of GCA [[Ponte](#), 2015]. Taken together, these findings suggest that ultrasound imaging may provide a useful diagnostic and biomarker approach for assessing and monitoring disease activity in GCA.

Currently, no valid biomarkers exist to assess response to therapy and to predict relapse. Changes in the conventional inflammatory markers (CRP and ESR) do not consistently reflect disease activity [[Tse](#), 1998]. Therefore, the utility of US in monitoring disease activity in GCA will be explored in a cohort of study subjects from select participating centers by sonographers trained and/or qualified as proficient in US imaging.

Longitudinal changes in vascular inflammation of the temporal and axillary arteries and the predictive value of US for disease activity will be assessed.

### **7.9.2. Synopsis**

A cohort of subjects with new onset GCA from participating imaging centers who have consented to participate in the US imaging portion of this study will be evaluated. These subjects will undergo US scans of their temporal and axillary arteries at the specified time points for assessment of changes in vascular inflammation.

Only subjects with newly diagnosed GCA are eligible to participate. Due to the exploratory nature of this portion of the study, there is no pre-specified sample size for this cohort. However, it is estimated that up to 50 subjects may participate.

Subjects will have an initial baseline scan at Screening and assessments at Baseline (Week 0), Weeks 12 and 52. Additional US scans should also be conducted in the event of relapses or flares, including flares/relapses that occur during Part B of the study. US scanning for flares/relapses in Part B of the study will conclude when the last subject in the US imaging cohort completes Part A of the study. Thereafter, no additional scans will be taken.

Subjects may also be asked to provide retrospective consent for assessment of their diagnostic US scan. Efforts should be made to conduct the baseline US scan within 3 days of initiating prednisone therapy. However, inability to comply with this time frame does not exclude subjects from participation. Data will be analyzed according to the time frame between prednisone dose and US scan. Detailed information on US imaging in this cohort of study subjects is included in [Appendix 8](#).

## **8. DATA MANAGEMENT**

- For this study (eDM) subject data will be entered into GSK defined CRFs, transmitted electronically to GSK or designee and combined with data provided from other sources in a validated data system.
- Management of clinical data will be performed in accordance with applicable GSK standards and data cleaning procedures to ensure the integrity of the data, e.g., removing errors and inconsistencies in the data.
- Adverse events and concomitant medications terms will be coded using MedDRA (Medical Dictionary for Regulatory Activities) and an internal validated medication dictionary, GSKDrug.
- CRFs (including queries and audit trails) will be retained by GSK, and copies will be sent to the investigator to maintain as the investigator copy. Subject initials will not be collected or transmitted to GSK according to GSK policy.

## 9. STATISTICAL CONSIDERATIONS AND DATA ANALYSES

### 9.1. Hypotheses

The primary null hypothesis (H0) for this study is that there is no difference between sirukumab 100mg SC q2w plus 6 month prednisone (Treatment Arm A) and placebo plus 6 month prednisone (Treatment Arm D) in the proportions of subjects with sustained disease remission at 52 weeks.

The alternative hypothesis (H1) for this study is that there is a difference in the proportions of subjects with sustained disease remission at 52 weeks.

The hypothesis to be tested for the proportion of subjects in sustained disease remission at 52 weeks using a 2-sided test at  $\alpha=0.05$  will therefore be:

H0: Sirukumab 100mg SC q2w + 6 month prednisone = placebo + 6 month prednisone

Vs.

H1: Sirukumab 100mg SC q2w + 6 month prednisone  $\neq$  placebo + 6 month prednisone

